5.3. Analysis of safety and reactogenicity

5.3.1. Analysis of safety and reactogenicity planned in the protocol (Amended 03-DEC-2020)

The following safety analyses will be performed based on the Solicited Safety or Exposed Sets. The following safety analysis will be performed on the pooled data then the US and ex-US separately.

Endpoint	Statistical Analysis Methods
Primary	
(US + ex-US data to be pooled)
 
For each group with 1st dose vaccination of RSVPreF3 (two dose levels) when given alone or co-ad with dTpa; the following points will be analysed for 1st and 2nd dose vaccination.
 
The percentage of subjects with at least one local AE on left or right arm with at least one general AE and with any ("solicited or unsolicited") AE during the 7-day follow up period (the day of vaccination + 6 subsequent days) or 30 -day follow up period (the day of vaccination + 29 subsequent days) post 1st and 2nd vaccination period will be tabulated with exact 95% CI by study group. The same computations will be done for Grade 3 AEs, for any AEs considered related to vaccination, for Grade 3 AEs considered related to vaccination and for AEs resulting in medically attended visits.
 
The percentage of subjects reporting each individual solicited local AE (any grade, Grade 3 and those resulting in a medically attended visit) and solicited general AE (any grade, Grade 3, any related, Grade 3 related and those resulting in a medically attended visit) during the 7-day follow-up period (the day of vaccination + 6 subsequent days) will be tabulated based on maximum intensity for each group.
 
For fever, the number and percentage of subjects reporting fever by half degree (°C) cumulative increments during the 7-day follow-up period (the day of vaccination + 6 subsequent days) will be tabulated for each group. Similar tabulations will be performed for any fever with a causal relationship to vaccination, Grade 3 or above (> 39.0°C/102.2°F) causally related fever, and

Endpoint	Statistical Analysis Methods
	
fever resulting in a medically attended visit. In addition, the prevalence of any and Grade 3 fever will be presented graphically over time after each vaccination.
 
The percentage of subjects with any unsolicited AEs during the 30-day follow-up period (the day of vaccination + 29 subsequent days) with its exact 95% CI will be tabulated by group and by Medical Dictionary for Regulatory Activities (MedDRA) system organ classes (SOC) and preferred term. Similar tabulation will be done for Grade 3 unsolicited AEs, for any causally related unsolicited AEs, for Grade 3 causally related unsolicited AEs and for unsolicited AEs resulting in a medically attended visit and leading to withdrawal from study. The verbatim term of unsolicited AEs will be reviewed by a physician and the signs and symptoms will be coded according to the MedDRA Dictionary for Adverse Reaction Terminology.
 
The percentage of subjects with at least one report of SAE classified by the MedDRA SOC and Preferred Terms and reported during the 30-day follow-up period (the day of vaccination + 29 subsequent days) will be tabulated with exact 95% CI. SAEs will also be described in detail.
 
The percentage of subjects using concomitant medication (any medication, any antipyretic and any antipyretic taken prophylactically, respectively) during the 7-day follow-up period and during the 30-day follow-up period will be summarized by each group and pooled.

Secondary	
(US and ex-US data to be considered pooled, then separately)
 
For each group with 1st dose vaccination of RSVPreF3 (two dose level) when given alone or co-administered with dTpa; the following points will be analysed for 1st and 2nd dose vaccination.
 
The percentage of subjects with at least one local AE with at least one general AE and with any ("solicited or unsolicited") AE during the 7-day or 30 -day follow-up as well any SAE up period to 180 days post 1st and 2nd vaccination time points will be tabulated with exact 95% CI by study group. The same computations will be done for Grade 3 AEs, for any AEs considered related to vaccination, for Grade 3 AEs considered related to vaccination and for AEs resulting in medically attended visits and AEs leading to withdrawal from study.
 
The percentage of subjects with at least one report of SAE classified by the MedDRA SOC and Preferred Terms and reported during the 30-day or 180-day follow-up period will be tabulated with exact 95% CI for each formulation (US and ex-US).
 
The percentage of subjects reporting each individual solicited local AE on left or Right arms (any grade, Grade 3 and those resulting in a medically attended visit) and solicited general AE (any grade, Grade 3, any related, Grade 3 related and those resulting in a medically attended visit) during the 7-day follow-up period (i.e. on the day of vaccination and 6 subsequent days) will be tabulated based on maximum intensity for each group for each formulation (US and ex-US).
 
For fever, the number and percentage of subjects reporting fever by half degree (°C) cumulative increments during the 7-day follow-up period will be tabulated for each group for each formulation (US and ex-US). Similar tabulations will be performed for any fever with a causal relationship to vaccination, Grade 3 or above ($> 39.0^{\circ}\text{C}/102.2^{\circ}\text{F}$) causally related fever, and fever resulting in a medically attended visit. In addition, the prevalence of any and Grade 3 fever will be presented graphically over time after each vaccination.
 
For each formulation (US and ex-US), the percentage of subjects with any unsolicited AEs during the 30-day follow-up period (i.e. on the day of vaccination and 29 subsequent days) with its exact 95% CI will be tabulated by group and by Medical Dictionary for Regulatory Activities (MedDRA) SOC and preferred term. Similar tabulation will be done for Grade 3 unsolicited AEs, for any causally related unsolicited AEs, for Grade 3 causally related unsolicited AEs and for unsolicited AEs resulting in a medically attended visit. The verbatim term of unsolicited AEs will


Endpoint	Statistical Analysis Methods
	be reviewed by a physician and the signs and symptoms will be coded according to the MedDRA Dictionary for Adverse Reaction Terminology.
Tertiary	Will be described in a Statistical Analysis Plan finalised before database unblinding/freezing.

5.3.2. Additional considerations

5.3.2.1. Analysis of solicited events

The analysis of solicited events will be performed on Solicited Safety Set. The intensity of the following solicited events will be assessed as described:

Table 5 Intensity scales for solicited symptoms in adults

Adults/Child (≥6 years)		
Adverse Event	Intensity grade	Parameter
Pain at injection site	CC1 - This section contained Clinical Outcome Assessment data collection questionnaires or indices, which are protected by third party copyright laws and therefore have been excluded.	
Redness at injection site		
Swelling at injection site		
Temperature*		
Headache		
Fatigue		
Gastrointestinal symptoms (nausea, vomiting, diarrhoea and/or abdominal pain)		

CC1 - This section contained Clinical Outcome Assessment data collection questionnaires or indices, which are protected by third party copyright laws and therefore have been excluded.

The maximum intensity of solicited administration site redness/swelling will be scored at GSK Biological as follows:

CCI - This section contained Clinical Outcome Assessment data collection questionnaires or indices, which are protected by third party copyright laws and therefore have been excluded.

Duration in days of solicited local and general adverse events within 7 days after vaccination will be tabulated by study group and overall, and if needed by age group. The derivation rule of duration in days for solicited events is detailed in section [10.1.3.9](#).

5.3.2.2. Analysis of Unsolicited Adverse Events

The analysis of unsolicited events will be performed on Exposed Set.

5.3.2.3. Combined Solicited and Unsolicited Adverse Events

The combined analysis of solicited and unsolicited events will be performed on Exposed Set. A summary of subjects with all combined solicited and unsolicited adverse events will be provided.

Solicited adverse events will be coded by MedDRA as per the following codes

Solicited symptom	Lower level term code	Corresponding Lower level term decode
Pain	Injection site pain	10022086
Redness	Injection site redness	10022098
Swelling	Injection site swelling	10053425
Fatigue	Fatigue	10016256
Fever	Fever	10016558
Headache	Headache	10019211
Gastrointestinal symptoms [†]	Gastrointestinal disorder	10017944

Please note – to check for AE term in CDISC during dry run

[†]Gastrointestinal symptoms include nausea, vomiting, diarrhoea and/or abdominal pain.

For [clintrial.gov](#) and [EudraCT](#) posting purposes, a summary of combined solicited and unsolicited adverse events will be produced by System Organ Class and preferred terms and according to occurrence of each event.

5.3.2.4. Other analysis

Other safety analysis will be performed on Exposed Set.

Concomitant medications/products will be coded using the GSKDRUG dictionary. The number and percentage of subjects taking concomitant medications (any medication, any antipyretic and any antipyretic taken prophylactically, respectively) within 7 days following vaccination, 30 days following vaccination and 12 months following vaccination will be summarized by group. A listing will also be provided.

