**CONFIDENTIAL**

209141 (RSV MAT-011)  
Protocol Amendment 6 Final

\*All subject groups will be given RSV 120mcg and subjects will be followed in an unblinded open label manner

\*\* Hematological and biochemical laboratory testing at Visit 4 (D -7 up to and including 2nd dose vaccination) at the investigator's discretion

\*\*\* There will be no follow-up between C1 and V4. New medical history and relevant new safety events during this period will be recorded at visit 4 for subjects who agree to the study extension and sign the informed consent addendum.

**CONFIDENTIAL**209141 (RSV MAT-011)  
Protocol Amendment 6 Final

The study will be conducted with 2 formulations of dTpa, dTpa\_300 (in the US) and dTpa\_500 (ex-US).

Approximately 500 eligible subjects (250 in the US and 250 ex-US) will be enrolled. Of these, approximately 250 subjects will be randomized to 5 US study groups in a 1:1:1:1:1 ratio using SBIR, and the remaining approximately 250 will be randomized to 5 ex-US study groups in a 1:1:1:1:1 ratio using SBIR. The randomization algorithm will use a minimization procedure by treating study formulation (US and ex-US) as a stratification factor, and age at the time of vaccination (18-32 or 33-45 years of age) and center as minimization factors.

Protocol waivers or exemptions are not allowed unless necessary for the management of immediate safety concerns. Therefore, adherence to the study design requirements, including those specified in the schedule of activities (Section 2), are essential and required for study conduct.

- Type of study: self-contained
- Experimental design:
  - Primary Vaccination: multi-centric study, multi-country Phase II, observer-blind, randomized, with 5 parallel groups in each formulation (US, ex-US).
- Study Extension: multi-centric study, multi-country Phase II, open unblinded, with all 5 parallel groups in each formulation (US, ex-US) receiving the experimental RSV maternal (120 $\mu$ g) vaccine.
- Duration of the study: The primary study will be approximately 6 months for each enrolled subject and from 18 up to 24 months for subjects that agree to participate in the study extension.
  - Primary Vaccination
    - Epoch 001: Screening
    - Epoch 002: Primary vaccination starting at Visit 1 (Day 1) and ending just before the Visit 3 (Day 31)
    - Epoch 003: Follow-up after Visit 3 (Day 31) to Phone Contact 1 on (Day 181)

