**7.4.2. Replacement of unusable vaccine(s) doses**

In addition to the vaccine doses provided for the planned number of subjects (including over-randomisation when applicable), at least 10% additional vaccine doses will be supplied to replace those that are unusable.

The investigator will use SBIR to obtain the replacement product number. The replacement numbers will be allocated by component. The system will ensure, in a blinded manner, that the replacement product matches the formulation the subject was assigned to by randomisation.

**CONFIDENTIAL**209141 (RSV MAT-011)  
Protocol Amendment 6 Final**7.5. Concomitant medication(s)/product(s) and concomitant vaccinations****7.5.1. Recording of concomitant medications/products and concomitant vaccinations**

At each study visit/contact, the investigator or delegate should question the subject about any medications/products taken and vaccinations received by the subject.

The following concomitant medication(s)/product(s)/vaccine(s) must be recorded in the eCRF.

- All concomitant medications/products, except vitamins and dietary supplements, administered during the period of 31 days post primary vaccination and 2nd vaccination.
- Any concomitant vaccination administered in the period starting 30 days before the dose of study vaccine(s) and ending at the last study visit/contact (Day -30 to Day 181 post 2nd vaccination).
- Prophylactic medication (i.e. medication administered in the absence of ANY symptom and in anticipation of a reaction to the vaccination).

An anti-pyretic is considered to be prophylactic when it is given in the absence of fever and any other symptom, to prevent fever from occurring fever is defined as temperature. 38.0°C/100.4°F regardless the location of measurement. The preferred location for measuring temperature in this study will be the oral cavity.

- Any concomitant medications/products/vaccines leading to the withdrawal or non-eligibility of the subject from the study.
- Any concomitant medications/products/vaccines relevant to an SAE to be reported as per protocol or administered at any time during the study period for the treatment of an SAE. In addition, concomitant medications relevant to SAEs need to be recorded on the expedited Adverse Event report.
- Any antipyretic administered in the period starting 6 hours before vaccination and ending 12 hours after vaccination needs to be recorded on the specific page of the eCRF.

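### The SAP tabulates medication and antipyretic use over 12 months, but the protocol records all medications for only 31 days after each dose, so those percentages would be understated

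*SAP*

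**What the plan says.** SAP 5.3.2.4 (Other analysis) covers three categories: "any medication, any antipyretic and any antipyretic taken prophylactically, respectively". For each, the number and percentage of users "within 7 days following vaccination, 30 days following vaccination and 12 months following vaccination will be summarized by group". The analysis set is the Exposed Set, and a listing accompanies the table.

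Protocol 7.5.1 defines what is recorded in the eCRF. The general rule is "All concomitant medications/products, except vitamins and dietary supplements, administered during the period of 31 days post primary vaccination", with the same period after the second vaccination. Other bullets reach beyond that period, but only for selected categories:

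- vaccinations: "Any concomitant vaccination administered in the period starting 30 days before the dose of study vaccine(s) and ending at the last study visit/contact";
- products tied to an SAE: "Any concomitant medications/products/vaccines relevant to an SAE to be reported as per protocol", or given to treat one;
- products leading to withdrawal or non-eligibility;
- prophylactic medication, defined by its being given in anticipation of a reaction to vaccination.

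A separate antipyretic rule is narrower still: "Any antipyretic administered in the period starting 6 hours before vaccination and ending 12 hours after vaccination needs to be recorded".

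On follow-up, the notes to Figure 1 in protocol 5.2 state: "There will be no follow-up between C1 and V4". C1 is the Day 181 phone call; V4 is the visit before the second dose. The main medication summary in SAP 5.3.1 is planned only "during the 7-day follow-up period and during the 30-day follow-up period will be summarized by each group and pooled", and protocol 10.3.4 plans the same two windows.

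**The concern.** A percentage of women using a medication within 12 months means what it says only if use was recorded for 12 months. Here general recording stops after about one month. The table uses the Exposed Set, and the SAP has no rule restricting the denominator to women observed for the full period. A woman who took a medication in month four, outside the selected categories, would enter the table as a non-user.

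At stake is how one column of a descriptive safety table is read. The final analysis feeds the study report and public disclosure (SAP 7.1.1). A reader could take the 12-month column as actual medication and antipyretic use over a year in each group.

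**Working it through.** The plan gives no figure to reproduce, so the check compares what is tabulated with what is recorded.

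**1. Could the Schedule of Activities widen the recording rule?** It marks recording of concomitant medications and vaccinations at Phone Contact 1, Visit 4 and Phone Contact 3. Its footnote 8 defers to Section 7.5, so the marks show when women are asked, and 7.5.1 decides what is recorded. The 31-day limit stands.

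**2. Share of the window with full recording.** Inputs: 31 days (protocol 7.5.1) and 12 months taken as 365 days. 31/365 = 8.5%. The 7- and 30-day windows lie wholly inside the 31 days, so their coverage is 100%.

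**3. Follow-up after dose 1.** Phone Contact 1 falls at 165–195 days (protocol Table 4). The part of the year after it is 365 − 195 = 170 to 365 − 165 = 200 days, essentially all of it without follow-up. At Visit 4, protocol 8.3.2 has the site review significant medical conditions and vaccinations from the gap, not all medications, and only for women entering the extension. Women who do not join end at the Day 181 call (protocol 5.4 and 9.1).

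**4. Follow-up after dose 2, if the window applies there.** The last contact is at 165–195 days: 165/365 = 45% to 195/365 = 53% of a year. The rest is never observed.

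**5. Which rows are affected.**

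| Row | Recorded after 31 days? | Effect on the 12-month column |
|---|---|---|
| Any medication | Selected categories only | Understated |
| Any antipyretic | Only if in a selected category | Understated |
| Prophylactic antipyretic | No end date stated, but tied to vaccination by definition | Redundant, not evidently low |

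**6. Direction and possible size.** The direction is downward for the first two rows. The size depends on usage rates that the documents do not give. As an illustration only, let p be the true 31-day use (an assumption). With a constant, independent rate, 12-month use would be 1 − (1 − p)^(365/31). If use after the first 31 days ran at one fifth of that rate (also an assumption), it would be 1 − (1 − p)^(1 + 0.2 × 334/31), where 334 = 365 − 31.

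| Assumed 31-day use | 12-month use, constant rate | 12-month use, one-fifth rate later |
|---|---|---|
| 5% | 45% | 15% |
| 10% | 71% | 28% |
| 20% | 93% | 51% |
| 40% | 99.8% | 80% |

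Under either assumption the table would show roughly the first column plus whatever the selected categories add. The spread between the scenarios shows why no single figure can be given.

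**The case against.** The strongest reply is that this is stale text of little weight. The 21 October 2019 SAP gave 6 months here and the Amendment 3 SAP gave 12. Protocol Amendment 2 had added follow-up to Day 365 and Amendment 3 withdrew it. Carry-over is the likeliest explanation, though that is an inference. Medication use is in no objective or endpoint, a listing accompanies the table, and the table layouts are in a separate document (SAP 10.2) that may already differ. All of this stands, and it makes the matter minor. It does not reconcile the current SAP with protocol 7.5.1, and SAP Section 8 does not list the 12-month summary as a change from the planned analyses.

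Four stronger readings are tempting but go beyond the documents:

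- **A reader might infer that later entries would come mainly from women with SAEs, so that group differences in them reflect SAE recording.** Nothing gives that mix. Vaccinations are recorded to the last contact, and protocol 8.3.2 has gap-period vaccinations reported as concomitant medications. The SAP does not say whether they count as any medication; if they do, they could outnumber SAE-related entries.
- **A reader might infer that all three rows are falsely low.** The prophylactic row is not evidently so.
- **A reader might take 8.5% as the size of the bias.** It is the share of days with full recording, not the error in a percentage of users.
- **A reader might infer that a 12-month table after dose 2 is promised.** SAP 5.3.2.4 refers to vaccination without saying which dose, so this is an ambiguity.

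**Conclusion.** The SAP asks for 12-month percentages that the protocol's data collection cannot support. On the current text, the any-medication and any-antipyretic figures would be understated after dose 1, because full recording covers 8.5% of the window and the second half of the year has essentially no follow-up. The amount cannot be derived from the documents. If the window is read as applying to dose 2 as well, it is unobservable.

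The conclusion assumes that sites follow protocol 7.5.1 as written and that the table is produced on the full Exposed Set as SAP 5.3.2.4 states. It is a minor correction to one descriptive table. The 7- and 30-day columns are sound, and no endpoint or safety or immunogenicity conclusion depends on the 12-month column.

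**What to change.** Delete the 12-month window from SAP 5.3.2.4. The 7- and 30-day windows remain, matching protocol 10.3.4 and SAP 5.3.1, which already call for analysis of both the first and the second vaccination.

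If a later-period summary is wanted, restrict it to the categories collected after 31 days (vaccinations, SAE-related products, products leading to withdrawal or non-eligibility, prophylactic medication). Label it as such, state the period actually observed, and say whether vaccinations are counted.

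The cost is one phrase of SAP text and one fewer table column. No data are lost and nothing changes at the sites.

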6. ANALYSIS INTERPRETATION

All comparative analyses will be descriptive with the aim to characterise the difference in immunogenicity between groups. These descriptive analyses should be interpreted with caution considering that there is no adjustment for multiplicity for most of these comparisons.

7. CONDUCT OF ANALYSES

7.1. Sequence of analyses

7.1.1. First and final study

Analyses to evaluate objectives and endpoints will be performed in steps.

- A **first analysis** will be performed on all data available and as clean as possible, when data for at least primary and secondary endpoints pertaining to safety and immunogenicity up to Day 31 are available. At this point, the statistician will be unblinded (i.e. individual subject treatment assignments will be available), but no individual listings will be provided to the study team. Given that summary safety results may unblind some specific subjects, the study will be considered as single-blind from this point onwards, subjects and investigators will be unblinded after Day 181 post 1st vaccination. The investigators will be provided with the individual data listings or with the randomization listings after Day 181.
- The **second analysis** will evaluate safety data and will be performed when **all subjects** have completed visits up to (and including) C1 (Day 181) and the data are available. From this point the study is unblinded and will continue as an open label study.
- The **third analysis** will evaluate safety and immunogenicity data and will be performed when **all subjects** have completed visits up to (and including) Visit 6 (Day 31 post 2nd dose vaccination) and the data are available. At this time, any available safety data will also be provided.
- The final end-of-study will be performed when all data for at least primary and secondary endpoints up to study conclusion at Day 181 post 2nd dose vaccination (C3) are available. An integrated clinical study report containing all available data will be written and made available to the investigators

The final study report will contain at least the final analyses of all primary and secondary endpoints. these analyses will be documented in an amended study report. If the data for tertiary endpoints become available at a later stage, (an) additional analysis/ analyses will be performed.

Description	Disclosure Purpose (CTRS=public posting, SR=study report, internal)
First Analysis (E1_02)	Internal, Public disclosure
Second Analysis (E1_03)	Internal
Third Analysis (E1_04)	Internal
Final Analysis (E1_01)	Public disclosure, Study report

